## **7 Subject Selection and Withdrawal**

### **7.1 *Inclusion Criteria***

In order to be eligible to participate subjects must meet all of the following criteria:

1. Men and women age:  $\geq 18$  years and  $< 65$  years of age.
2. Weight:  $\geq 45$  kilograms.
3. DBA diagnosed according to the DBA criteria (Vlachos, 2008) (Appendix B).
4. RBC transfusion-dependence (defined as 2 units packed RBCs per 28 days averaged over 84 days [12 weeks] prior to study entry) (Gale, 2011) (Appendix C).
5. Calculated creatinine clearance  $\geq 30$  mL/min (Appendix D).
6. Karnofsky performance status scale score  $\geq 70$  (Appendix E).
7. Female subjects of childbearing potential participating in the study are to use highly effective methods of birth control (abstinence, oral contraceptives, barrier method with spermicide or surgical sterilization) during study participation and for 1 week following the last dose of TFP (a total of 4 weeks of the study). Female subjects of childbearing potential must have a negative serum  $\beta$ -human chorionic gonadotropin pregnancy test within 3 days prior to the start of TFP given on Day 1. Subjects must be counseled concerning measures to be used to prevent pregnancy and potential toxicities prior to the first dose of TFP. A female subject of childbearing potential is a sexually mature woman who has not undergone a hysterectomy or bilateral oophorectomy; or who has not been postmenopausal for at least 24 consecutive months (i.e., who has had menses at some time in the preceding 24 months).
8. Male subjects must agree to use a latex condom during any sexual contact with females of childbearing potential while participating in the study and for 1 week following the last dose of TFP, even if he has undergone a successful vasectomy (a total of 4 weeks of the study). Male subjects must be counseled concerning measures to be used to prevent pregnancy and potential toxicities prior to the first dose of TFP.
9. Agreement to adhere to the study visit schedule, understand and comply with all protocol requirements.
10. The subjects are capable of giving informed consent.

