## **8.2 Treatment Regimen**

Trifluoperazine will be given orally once daily as 1 mg, 2 mg (two 1mg tablets), 5 mg, or 10 mg (two 5mg tablets). The treatment duration will be up to 21 days (3 weeks).

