#### **9.4 Visit 3**

Visit 3 will be Day 22 ( $\pm 2$  days) of the study. The subject will undergo full safety analysis, including a physical examination (including weight, vital signs, blood pressure and neurological exam). Karnofsky performance status will be assessed. Blood work will be performed for a complete blood count (CBC; RBC count, hemoglobin, hematocrit, absolute reticulocyte count, white blood cell count, absolute neutrophil count, and platelet count), serum chemistry panel for hepatic and renal function (blood urea nitrogen, creatinine, bilirubin [total and direct], aspartate aminotransferase [AST], and alanine aminotransferase [ALT]), and pharmacodynamic marker analysis, if applicable (Appendix J). If the subject is a female, menstrual status will be assessed. Transfusion history will be documented. The subject will be questioned and evaluated for any adverse events. All concomitant therapies will be documented.

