## 10 Risks to Subjects

Adverse reactions with TFP include drowsiness, dizziness, skin reactions, rash, dry mouth, insomnia, amenorrhea, fatigue, muscular weakness, anorexia, lactation, blurred vision, and neuromuscular (extrapyramidal) reactions. Details regarding extrapyramidal and other adverse reactions with TFP follow:

- **Neuromuscular (Extrapyramidal) Reactions:** These symptoms are characterized by motor restlessness. They may be of the dystonic type, or they may resemble Parkinsonism (described below).
- **Motor Restlessness:** Symptoms may include agitation or jitteriness and sometimes insomnia. These symptoms often disappear spontaneously.
- **Dystonia (Class Effect):** Symptoms of dystonia, prolonged abnormal contractions of muscle groups, may occur in susceptible individuals during the first few days of treatment. Dystonic symptoms include spasm of the neck muscles, sometimes progressing to tightness of the throat, swallowing difficulty, difficulty breathing, and/or protrusion of the tongue. While these symptoms can occur at low doses, they occur more frequently at higher doses of first generation antipsychotic drugs.
- **Pseudoparkinsonism:** Symptoms may include mask-like facies, drooling, tremors, pill-rolling motion, cogwheel rigidity, and shuffling gait.
- **Tardive Dyskinesia:** Tardive dyskinesia is a rare syndrome characterized by rhythmical involuntary movements of the tongue, face, mouth, or jaw (e.g., protrusion of tongue, puffing of cheeks, puckering of mouth, chewing movements). These symptoms may be accompanied by involuntary movements of extremities. In rare instances, these involuntary movements of the extremities are the only manifestations of tardive dyskinesia. Symptoms may persist for months or years and, while they gradually disappear in some subjects, they may be irreversible in others. The risk appears to be greatest in elderly subjects (especially women) on prolonged, high-dose therapy. There is no known effective treatment for tardive dyskinesia. It has been reported that fine vermicular movements of the tongue may be an early sign of the syndrome and if the medication is stopped at that time the syndrome may not develop.
- **Adverse Reactions Reported with TFP or Other Phenothiazine Derivatives:** Adverse effects with different phenothiazines vary in type, frequency, and mechanism of

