dermatitis); other allergic reactions (asthma, laryngeal edema, angioneurotic edema, anaphylactoid reactions); peripheral edema; reversed epinephrine effect; hyperpyrexia; increased appetite; increased weight; a systemic lupus erythematosus-like syndrome; pigmentary retinopathy; with prolonged administration of substantial doses, skin pigmentation, epithelial keratopathy, and lenticular and corneal deposits.

- Electrocardiogram changes, particularly nonspecific, usually reversible Q and T wave distortions, have been observed in some subjects receiving phenothiazine antipsychotics.

There have been occasional reports of sudden death in subjects receiving phenothiazines. In some cases, the cause appeared to be cardiac arrest or asphyxia due to failure of the cough reflex.

The effects of TFP on fertility or a fetus are not known. The side effects of TFP on newborns are also not known, therefore breastfeeding will not be allowed on the study. The subject will be removed from the study if she becomes pregnant during the study.

Adult subjects with DBA who are on chronic transfusion therapy may have iron overload despite iron chelation or due to non-compliance. Iron overload can lead to liver dysfunction (liver function test elevations initially and eventual fibrosis and cirrhosis), cardiac dysfunction (arrhythmias and eventual heart failure), and endocrine dysfunction (hypothyroidism, diabetes mellitus, growth hormone deficiency, hypogonadism, premature ovarian failure, etc.). If such dysfunction is documented but is adequately addressed, then these subjects will be eligible for this study. If any of these potential side effects occur for the first time while on the subject is on the study drug, the event will be treated as an adverse event (AE).

Subjects with DBA have RBC aplasia, thus necessitating transfusion therapy. As this is a bone marrow failure syndrome these subjects also can have other cytopenias including neutropenia and thrombocytopenia, and often pancytopenia (not necessarily consistent with aplastic anemia). The eligibility criteria for entry into the study allow mild abnormalities in all the cell lines, but subjects with severe cytopenia are ineligible.

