**Serious Adverse Event**

A serious adverse event (SAE) is one that at any dose (including overdose):

- Results in death
- Is life-threatening
- Requires inpatient hospitalization or prolongation of existing hospitalization
- Results in persistent or significant disability or incapacity
- Results in a congenital anomaly or birth defect
- Is an important medical event

Important medical events are those that may not be immediately life threatening, but are clearly of major clinical significance. They may jeopardize the subject, and may require intervention to prevent one of the other serious outcomes noted above.

An overdose, accidental or intentional, whether or not it is associated with an AE, or abuse, withdrawal, sensitivity or toxicity to an investigational product should be reported as an AE. If an overdose is associated with an AE, the overdose and adverse event should be reported as separate terms.

All subjects will be monitored for AEs during the study. Assessments may include monitoring of any or all of the following parameters: the subject's clinical symptoms, laboratory, pathological, radiological or surgical findings, physical examination findings, or other appropriate tests and procedures.

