#### ***Adverse Event Reporting Period***

All AEs will be recorded by the Investigator from the time the subject signs informed consent to 7 days after the last dose (completion of the 4th week). AEs and SAEs will be recorded on the AE page of the CRF and in the subject's source documents. All SAEs must be reported within 24 hours of the Investigator's knowledge of the event by facsimile, or other appropriate method, using the SAE Report Form, or approved equivalent form.

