## 22.1 Appendix A continued

\*Historical clinical laboratory evaluations performed for medical evaluation within 28 days are acceptable for study entry.

- a: All Day 1 assessments are to be done prior to TFP administration. TFP should be initiated within 7 days following a blood transfusion.
- b: Hematology laboratory evaluations (RBC count, hemoglobin, hematocrit, absolute reticulocyte count, white blood cell count, absolute neutrophil count, and platelet count) will be collected at Screening and at subsequent visits during the Treatment and Follow-Up Periods, as referenced in the schedule above. Any laboratory evaluations may be repeated more frequently if clinically indicated.
- c: Serum chemistry laboratory evaluations (blood urea nitrogen, creatinine, bilirubin [total and direct], aspartate aminotransferase [AST], alanine aminotransferase [ALT]) will be collected at Screening and at subsequent visits during the Treatment and Follow-Up Periods, as referenced in the schedule above. Any laboratory evaluations may be repeated more frequently if clinically indicated.
- d: Blood for pharmacodynamic disease marker analysis will be shipped to supporting company (see Appendix F).
- e: Females of childbearing potential: A female of childbearing potential is a sexually mature woman who has not undergone a hysterectomy or who has not been postmenopausal for at least 24 consecutive months (i.e., who has had menses at some time in the preceding 24 months). A serum pregnancy test (which must be negative) must be performed not more than 3 days from the start of TFP administration (Study Day 1). Subjects must agree to use highly effective methods of birth control during study participation and for at least 1 week following the last dose of TFP. Subjects must be counseled concerning measures to be used to prevent pregnancy and potential toxicities prior to the first dose of TFP. Serum pregnancy tests will be performed according to the above schedule during study participation.
- f: Subjects must have documented transfusion history for > 12 weeks before inclusion/initiation of treatment.

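### No pregnancy test is scheduled after Day 11, although dosing runs to Day 21 and contraception is required to about Day 28

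*Combined protocol and SAP*

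**What the plan says.** **Exposure.** Section 8.2 sets the course: "The treatment duration will be up to 21 days (3 weeks").

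**Contraception.** Section 7.1, item 7, requires it of women of childbearing potential "during study participation and for 1 week following the last dose of TFP (a total of 4 weeks of the study"). The same item requires a negative serum test within 3 days before Day 1.

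**Testing.** Appendix A ticks the pregnancy-test row at Screening, Visit 1 and Visit 2 (Day 11 ±1) and leaves it blank at Visit 3 (Day 22 ±2) and Visit 4 (Day 29 ±2). Sections 9.1 to 9.5 agree. For Visit 3, Section 9.4 says: "If the subject is a female, menstrual status will be assessed". Section 9.5 gives Visit 4 neither a test nor a menstrual check. Blood is drawn at both visits.

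**Risk.** Section 10 states: "The effects of TFP on fertility or a fetus are not known". It requires removal of a subject who becomes pregnant. Section 3.2.2 notes that metabolites cross the placenta. Section 10 also lists adverse reactions including "insomnia, amenorrhea, fatigue", and gives menstrual irregularities and false-positive pregnancy tests as class effects.

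**Reporting.** In Section 15.1 one criterion for a serious event is: "Results in a congenital anomaly or birth defect". Routine recording of adverse events runs from consent "to 7 days after the last dose".

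**Entry note.** The pregnancy-test row in Appendix A also carries an asterisk, explained as: "Historical clinical laboratory evaluations performed for medical evaluation within 28 days are acceptable for study entry". Footnote e to the same row sets a 3-day limit.

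**The concern.** The protocol treats pregnancy as a risk until a week after the last dose, but scheduled testing stops about halfway through dosing. Between Visit 2 and the end of the study, the removal rule in Section 10 can act only on a pregnancy that comes to light some other way.

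The menstrual check at Visit 3 is a weak substitute. A missed period on this drug may be a drug effect, so it does not separate pregnancy from the listed reactions. A conception late in the course may not yet have delayed a period at all.

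Safety is the only objective in Section 4. If a conception on drug is not looked for systematically, a report of no pregnancies partly reflects the schedule.

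**Working it through.** **The plan's own figure.** Contraception period = 21 dosing days + 7 days = 28 days = 4 weeks. This reproduces the 4 weeks in Section 7.1, item 7.

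**Without any assumption about the test.** The last test is on Day 11.
- Dosing days after it: 21 − 11 = 10, and 10/21 = 48%.
- Contraception days after it: 28 − 11 = 17, and 17/28 = 61%.

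No scheduled test can find a conception on those days, however sensitive it is.

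**With a detection lag.** Let L be the days from conception to a positive serum test. The documents give no value, so L = 6 to 14 days is an assumption, shown as a range. A last test on day T finds a conception on day c if c + L ≤ T. Hence:

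dosing days covered = min(21, T − L), and not below 0.

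| Last test | L = 6 | L = 8 | L = 10 | L = 14 |
|---|---|---|---|---|
| Day 10 (early edge of Visit 2) | 4 | 2 | 0 | 0 |
| Day 11 (Visit 2) | 5 | 3 | 1 | 0 |
| Day 12 (late edge of Visit 2) | 6 | 4 | 2 | 0 |
| Day 22 (Visit 3) | 16 | 14 | 12 | 8 |
| Day 29 (Visit 4) | 21 | 21 | 19 | 15 |

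As planned, with the ±1 day window, coverage is 0 to 6 of 21 dosing days (0% to 29%). At the longest lags the Day 11 test finds only conceptions from before the first dose.

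A last test on Day 22 would cover 8 to 16 dosing days (38% to 76%). A last test on Day 29 would cover 15 to 21 (71% to 100%). Over the full contraception period, Day 29 covers 29 − 14 = 15 to 29 − 6 = 23 of 28 days, so it does not close the gap completely.

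**The entry notes side by side.** The asterisk accepts laboratory results up to 28 days old for study entry. Item 7 and footnote e require a negative test within 3 days of starting the drug. All of these apply to the same row. The Visit 1 test, which Appendix A footnote a places before dosing, limits the practical effect.

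**The case against.** The strongest reply is that this is a design preference. Section 9 and Appendix A agree with each other, contraception and counselling are the stated preventive measures, and requiring contraception for longer than testing is not in itself a contradiction. Tests on Days 22 and 29 come after the last scheduled dose, so they would mainly identify exposure and do little to prevent it. All of this stands. It limits the point to a gap in ascertainment; it does not remove it.

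A reader might also infer three stronger things that the documents do not support.

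- **That the birth-defect criterion can never be met because testing stops on Day 11.** No birth outcome from a conception on drug falls within a 29-day study, whatever the test schedule. Under the heading on post-study adverse events, Section 15.1 also tells subjects to report later events they think related, and has the sponsor notified of possibly related events with no time limit. That route is passive, but it exists.
- **That the trial is bound to report no pregnancies.** The Day 11 test can find conceptions from before or shortly after Day 1. Menstrual status is asked at Visit 3, and adverse events are asked about at Visits 3 and 4. Drug-related amenorrhea makes a missed period ambiguous, but does not hide it.
- **That no pregnancy-reporting rule exists.** Most of Section 15.3, on sponsor and IRB notification, is absent from the text available for this review. Such a rule could stand there.

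On the asterisk, it can be argued that entry and start of drug are separate gates and that both notes can be met. That makes it a minor inconsistency, but the wording still needs to be settled.

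**Conclusion.** The point holds as a gap in safety surveillance. After Visit 2 no pregnancy test is scheduled, and 10 of 21 dosing days and 17 of 28 contraception days lie beyond it under any assumption. With an assumed lag of 6 to 14 days and the visit window, scheduled tests cover at most 6 of the 21 dosing days and possibly none. The remaining checks are a menstrual question that the drug's own effects make ambiguous, adverse-event questioning, and passive later reporting. A conception on study drug would therefore not be detected systematically.

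The percentages in the assumption-free step depend only on the protocol's days. The 0 to 6 range depends on the assumed lag. The number of women of childbearing potential among the 3 to 24 subjects is not stated, so the expected number of affected pregnancies cannot be given. The 3+3 rules and the sample size are unaffected.

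**What to change.** 1. Reconcile the pregnancy-test row of Appendix A and Sections 9.4 and 9.5 with the contraception period in Section 7.1, item 7. One way is to run the serum test on the blood already drawn at Visits 3 and 4; at Visit 4 the local laboratory could do it. The testing rule itself is for the sponsor to set. If the schedule stays as it is, the protocol should say why testing ends on Day 11, and the safety report should state that conceptions after about the first week of dosing were not tested for.
2. Reconcile the 28-day asterisk on that row with the 3-day limit in item 7 and footnote e.
3. Check whether the full Section 15.3 requires pregnancies to be reported and followed to outcome. If it does not, reconcile the birth-defect criterion in Section 15.1 with the 7-day recording period. A later test alone would not do this.

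**Cost.** Up to two assays per woman of childbearing potential, with no extra visit or blood draw. Even if all 24 subjects were such women, that is 2 × 24 = 48 assays. Because Section 10 lists false-positive tests as a class effect, some added results may be false positives, and the sponsor has to settle how to handle them. The other two items are changes of wording.

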#### **9.5 Visit 4**

Visit 4 will be Day 29 ( $\pm 2$  days) of the study (Follow-up Period). The subject will undergo post-treatment safety assessment including a physical examination and blood work (CBC and chemistry panel). Transfusion history will be documented. The subject will be questioned and evaluated for any adverse events. This visit may be done virtually through a system that can visually assess the subject for neurologic issues. Blood work may be done at a local laboratory.

## 10 Risks to Subjects

Adverse reactions with TFP include drowsiness, dizziness, skin reactions, rash, dry mouth, insomnia, amenorrhea, fatigue, muscular weakness, anorexia, lactation, blurred vision, and neuromuscular (extrapyramidal) reactions. Details regarding extrapyramidal and other adverse reactions with TFP follow:

- **Neuromuscular (Extrapyramidal) Reactions:** These symptoms are characterized by motor restlessness. They may be of the dystonic type, or they may resemble Parkinsonism (described below).
- **Motor Restlessness:** Symptoms may include agitation or jitteriness and sometimes insomnia. These symptoms often disappear spontaneously.
- **Dystonia (Class Effect):** Symptoms of dystonia, prolonged abnormal contractions of muscle groups, may occur in susceptible individuals during the first few days of treatment. Dystonic symptoms include spasm of the neck muscles, sometimes progressing to tightness of the throat, swallowing difficulty, difficulty breathing, and/or protrusion of the tongue. While these symptoms can occur at low doses, they occur more frequently at higher doses of first generation antipsychotic drugs.
- **Pseudoparkinsonism:** Symptoms may include mask-like facies, drooling, tremors, pill-rolling motion, cogwheel rigidity, and shuffling gait.
- **Tardive Dyskinesia:** Tardive dyskinesia is a rare syndrome characterized by rhythmical involuntary movements of the tongue, face, mouth, or jaw (e.g., protrusion of tongue, puffing of cheeks, puckering of mouth, chewing movements). These symptoms may be accompanied by involuntary movements of extremities. In rare instances, these involuntary movements of the extremities are the only manifestations of tardive dyskinesia. Symptoms may persist for months or years and, while they gradually disappear in some subjects, they may be irreversible in others. The risk appears to be greatest in elderly subjects (especially women) on prolonged, high-dose therapy. There is no known effective treatment for tardive dyskinesia. It has been reported that fine vermicular movements of the tongue may be an early sign of the syndrome and if the medication is stopped at that time the syndrome may not develop.
- **Adverse Reactions Reported with TFP or Other Phenothiazine Derivatives:** Adverse effects with different phenothiazines vary in type, frequency, and mechanism of

occurrence, i.e. some are dose-related, while others involve individual subject sensitivity. Some adverse effects may be more likely to occur, or occur with greater intensity, in subjects with special medical problems, e.g., subjects with mitral insufficiency or pheochromocytoma have experienced hypotension following recommended doses of certain phenothiazines.

- Neuroleptic malignant syndrome (NMS) has been reported in association with antipsychotic drugs. Cardinal features of NMS are hyperpyrexia, muscle rigidity, altered mental status (including catatonic signs), and evidence of autonomic instability (irregular pulse or blood pressure). Additional signs may include elevated creatine phosphokinase, myoglobinuria (rhabdomyolysis), and acute renal failure. NMS is potentially fatal and requires symptomatic treatment and immediate discontinuation of neuroleptic treatment.

- Not all of the following adverse reactions have been observed with every phenothiazine derivative, but they have been reported with one or more and should be borne in mind when drugs of this class are administered: extrapyramidal symptoms (opisthotonos, oculogyric crisis, hyperreflexia, dystonia, akathisia, dyskinesia, parkinsonism) some of which have lasted months and even years—particularly in elderly subjects with previous brain damage; grand mal and petit mal convulsions, particularly in subjects with electroencephalogram abnormalities or history of such disorders; altered cerebrospinal fluid proteins; cerebral edema; intensification and prolongation of the action of central nervous system depressants (opiates, analgesics, antihistamines, barbiturates, alcohol), atropine, heat, organophosphorus insecticides; autonomic reactions (dryness of mouth, nasal congestion, headache, nausea, constipation, obstipation, adynamic ileus, ejaculatory disorders/impotence, priapism, atonic colon, urinary retention, miosis and mydriasis); reactivation of psychotic processes, catatonic-like states; hypotension (sometimes fatal); cardiac arrest; blood dyscrasias (pancytopenia, thrombocytopenic purpura, leukopenia, agranulocytosis, eosinophilia, hemolytic anemia, aplastic anemia); liver damage (jaundice, biliary stasis); endocrine disturbances (hyperglycemia, hypoglycemia, glycosuria, lactation, galactorrhea, gynecomastia, menstrual irregularities, false-positive pregnancy tests); skin disorders (photosensitivity, itching, erythema, urticaria, eczema up to exfoliative

dermatitis); other allergic reactions (asthma, laryngeal edema, angioneurotic edema, anaphylactoid reactions); peripheral edema; reversed epinephrine effect; hyperpyrexia; increased appetite; increased weight; a systemic lupus erythematosus-like syndrome; pigmentary retinopathy; with prolonged administration of substantial doses, skin pigmentation, epithelial keratopathy, and lenticular and corneal deposits.

- Electrocardiogram changes, particularly nonspecific, usually reversible Q and T wave distortions, have been observed in some subjects receiving phenothiazine antipsychotics.

There have been occasional reports of sudden death in subjects receiving phenothiazines. In some cases, the cause appeared to be cardiac arrest or asphyxia due to failure of the cough reflex.

The effects of TFP on fertility or a fetus are not known. The side effects of TFP on newborns are also not known, therefore breastfeeding will not be allowed on the study. The subject will be removed from the study if she becomes pregnant during the study.

Adult subjects with DBA who are on chronic transfusion therapy may have iron overload despite iron chelation or due to non-compliance. Iron overload can lead to liver dysfunction (liver function test elevations initially and eventual fibrosis and cirrhosis), cardiac dysfunction (arrhythmias and eventual heart failure), and endocrine dysfunction (hypothyroidism, diabetes mellitus, growth hormone deficiency, hypogonadism, premature ovarian failure, etc.). If such dysfunction is documented but is adequately addressed, then these subjects will be eligible for this study. If any of these potential side effects occur for the first time while on the subject is on the study drug, the event will be treated as an adverse event (AE).

Subjects with DBA have RBC aplasia, thus necessitating transfusion therapy. As this is a bone marrow failure syndrome these subjects also can have other cytopenias including neutropenia and thrombocytopenia, and often pancytopenia (not necessarily consistent with aplastic anemia). The eligibility criteria for entry into the study allow mild abnormalities in all the cell lines, but subjects with severe cytopenia are ineligible.

In the present study, TFP will be investigated in subjects with DBA over a lower dose range than is generally employed in subjects with schizophrenia. The maximum anticipated daily dose will be 10 mg. In contrast, the usual initial adult dose of TFP for schizophrenia is 2 to 5 mg orally 2 times a day with a maintenance dose of 15 to 20 mg/day and a maximum dose of 40 mg/day. Therefore, more severe adverse reactions with TFP may be less likely to occur in the current study.

The only alternative to this treatment is not to participate in this trial. The subject will continue on transfusion therapy during this trial and be transfused every 3-4 weeks when the hemoglobin is less than 8 gm/dL as prior.

Given the serious potential side effects of chronic, often life-long transfusion therapy and the continuous need for chelation therapy, the risks of this short, 3-week study (plus 1 week follow-up) are reasonable for this subject population. The preliminary data from the zebrafish and mice models and information gained from this study will be proof-of-principle of the use of this drug in the treatment of DBA. If no significant toxicity to this drug is noted, the drug will be chemically altered as to not cross the blood-brain barrier and potentially be a viable treatment for DBA, without the untoward neurological side effects.

